7.1 DEMOGRAPHIC AND OTHER BASELINE CHARACTERISTICS

Only descriptive statistics are planned for this section of the report.

A table in the CTR will present the number of patients screened, entered and treated. The number of patients prematurely discontinuing trial medication will be shown with the treatment discontinuation decisions as well as primary reasons for discontinuation. The number and percent of patients completing the planned treatment period and the number of patients with treatment ongoing (only applicable for potential interim analyses) will also be presented. Where percentages are shown, the denominator will be the number of patients treated in each patient group.

Descriptive statistics as well as frequency counts will be provided for all demographic and baseline characteristics depicted in [Section 5.4.1](#). The CTR tables will show the relevant descriptive statistics (number and percent within categories; other descriptive statistics for continuous variables) by patient group.

7.4 PRIMARY OBJECTIVE ANALYSIS

The main objective is to assess the long-term safety and tolerability of nintedanib, on top of standard of care, in children and adolescents with clinically significant fibrosing Interstitial Lung Disease.

The primary endpoint is the incidence of treatment emergent adverse events over the whole trial. Only descriptive analyses will be performed. There will be no treatment comparison.

7.4.1 Main analysis

The number and frequency of patients with treatment-emergent adverse events by primary system organ class (SOC) and preferred term (PT), as described in [Section 7.8.1](#), will be displayed. The primary analysis will implement the While-on-Treatment strategy of handling intercurrent event (ICE) defined in [Section 6.3](#) and will be based on the treated set (TS).

[figure not shown]
7.5 SECONDARY OBJECTIVE ANALYSIS

7.5.1 Key secondary objective analysis

This section is not applicable as no key secondary endpoint has been specified in the protocol.

7.5.2 Secondary objective analysis

This section is not applicable as no secondary endpoint has been specified in the protocol.

7.6.3 Time-to-event endpoints

Separate Kaplan-Meier plots will be presented by patient group and overall (total group) for time-to-event in extension trial for endpoints defined in [Section 5.3.2](#). Kaplan Meier estimates and confidence intervals (using Greenwood variance formula) for the cumulated time-to-event rate will be calculated over the whole trial. No statistical test will be performed.

7.7 EXTENT OF EXPOSURE

Extent of exposure data will be summarised and presented over the whole trial (refer to [Section 5.4.3](#)).

A summary table showing the duration on treatment in extension trial in weeks (both mean and frequency in categories, see [Section 5.4.3](#)) and dose intensity will be presented.

A summary of treatment interruptions will be performed including number of patients with at least one interruption, number and reason of interruptions, as well as time to first interruption (both mean and frequency in categories, see [Section 5.4.3](#)). A similar summary will be performed for dose changes.

Median, Q1 and Q3 percentiles are calculated from the Kaplan-Meier curve for time to premature treatment discontinuation, time to first dose reduction and for time to first treatment interruption. No statistical tests will be performed.

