For all patients, during treatment period, dose is adjusted based on patient's weight. Dose reduction to the next lower dose is possible to manage adverse events. The lowest possible dose is 25 mg b.i.d. (50 mg daily).

Roll-over patients will be requested to stay in the trial for at least 156 weeks (until Visit 15). At week 156, roll-over patients who can be treated with nintedanib or alternative treatment options outside the clinical trial will have their EoT Visit instead of Visit 15.

The remaining roll-over patients will continue in the trial until nintedanib or alternative treatment options can be made available to them outside the clinical trial.

New patients will be requested to stay in the trial until the end of trial (with expected minimum treatment duration of 76 weeks), then patients will perform their EoT Visit and enter in the 28-days follow-up period off-treatment until End of Study Visit (EOS).

Exception: patients aged 21 years must complete the trial before their 22nd birthday. Consequently, a treatment duration of at least 3 years might not be reached by some patients aged 21.

Patients completing trial while being 21 years old, even with a treatment duration less than 3 years, will be considered as completed patients.

The overall end of trial will take place approximately when last roll-over patient is expected to reach 3 years of treatment () ensuring nintedanib or alternative treatment options (e.g., via marketing authorization, via compassionate use, or via similar process) will be available for all remaining patients (roll-over or new patients) outside the trial at this time.

At this time, all the remaining patients will perform their EoT Visit. For logistical reasons, it may be planned that EoT visit of all remaining patients will occur within 6 weeks before the planned date of Visit 15 of last roll-over patient. If regular scheduled visit is planned for a patient during this period of 6 weeks, then the patient will skip this regular visit and will perform directly the EoT visit instead. After the EoT visit, all remaining patients will enter a 4-week follow-up period.

Trial medication will be stopped prematurely if a reason for withdrawal is met (refer to [section 3.3.4](#)).

Roll-over patients will be considered as prematurely discontinued from trial treatment if they stop trial medication before week 156 (except at the age of 21).

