$$\text{Sum of all treatment interruption durations [days]}$$

Total dose [g] will be calculated as

$$\text{Sum of durations of exposure on } x \text{ g [days]} * 2 * x \text{ g,}$$

with x in 0.025, 0.05, 0.075, 0.1, 0.15 and summarised as continuous variable.

Dose intensity [%] will be calculated as the amount of drug actually administered divided by the amount of drug that would have been administered, i.e. dose xx mg bid (depending on the body weight) during the planned treatment period (or until study discontinuation), multiplied by 100%. Dose intensity will be summarised as continuous variable and in categories [%]:

- ≤ 30
- > 30 to 50
- > 50 to 90
- > 90 to < 100
- ≥ 100

Exposure-related time-to-event analyses will be performed for the following items:

- Time to first dose reduction (not due to weight-based adjustment) [days]^[1]
- Time to first treatment interruption [days]
- Time to premature treatment discontinuation [days]

^[1] Will only be calculated for patients who started the trial on full dose according to their weight bin at baseline.

Time-to-event [days] for exposure-related analyses is derived based on first trial drug intake as

$$\text{Date of event/censoring} - \text{Date of first trial drug intake [days]} + 1 \text{ day}$$

For the above mentioned time-to-event analyses patients with no such event occurred during the trial will be censored according to the mechanism for censoring as described in [Table 5.4.3: 1](#).

Table 5.4.3: 1 Censoring rules for exposure-related time-to-event analyses

Rule #	Situation	Outcome (Event/Censored)	Date of event/censoring
1	Patient had a documented event and the date of the event is known	Event	Earliest date of event
2	Patient had a documented event and the date of the event is unknown	Event	Imputed date of event (as defined in Section 6.6.3.3)
3	Patient had no documented event and already terminated trial drug (last intake on End of treatment eCRF page available)	Censored	Date of last trial drug intake
4	Patient neither had a documented event nor terminated trial drug permanently (only applicable for potential interim analyses)	Censored	Date of interim data snapshot

These times will also be summarised in categories [weeks] as defined for duration of exposure [weeks] above.

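### SAP 7.7 plans a mean for right-censored time to first interruption, which varies with follow-up and so differs between patient groups even when the risk is the same (minor)

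*SAP*

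**What the plan says.** SAP 5.4.3 defines three exposure-related times: to first dose reduction, to first interruption and to premature discontinuation. For these, "patients with no such event occurred during the trial will be censored according to the mechanism for censoring" in Table 5.4.3: 1; for a patient who has stopped trial drug without the event, the censoring date is that of last intake. The first of the three carries a restriction: "Will only be calculated for patients who started the trial on full dose according to their weight bin at baseline". The section closes: "These times will also be summarised in categories [weeks] as defined for duration of exposure [weeks] above". Those categories are 15 bins, from at most 2 weeks to more than 156 weeks.

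SAP 7.7 then plans a summary of interruptions, "as well as time to first interruption (both mean and frequency in categories" of 5.4.3), followed by: "A similar summary will be performed for dose changes". Neither section says whether the mean and the categories use all times or event times only. The next paragraph of 7.7 has: "Median, Q1 and Q3 percentiles are calculated from the Kaplan-Meier curve for time to premature treatment discontinuation, time to first dose reduction", and also time to first interruption. No tests are planned.

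SAP 7 shows results for Group 1 (initiated nintedanib), Group 2 (continued nintedanib) and overall. Group 1 holds the new patients and also parent-trial Part A placebo patients. Protocol 3.1 says roll-over patients "will be requested to stay in the trial for at least 156 weeks (until Visit 15"). New patients stay until the overall end of the trial, with an expected minimum of 76 weeks. Protocol 3.3 expects them to enter over 18 months.

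**The concern.** A plain mean of a right-censored time has two possible readings, and neither estimates the mean time to first interruption. If all times are averaged, a patient who never interrupted counts as interrupting on the last dose day. If only events are averaged, the result cannot exceed the follow-up, and it rises as follow-up lengthens.

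Because follow-up differs between the displayed groups, the mean differs too, with no difference in tolerability. The direction is awkward. Group 1 starts nintedanib, so a shorter mean there could be read as early intolerance among initiators when it reflects shorter observation. The report would also carry two conflicting figures for one variable, the mean and the Kaplan-Meier median.

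For dose changes the same applies only if the similar summary includes a mean time. The only such time that 5.4.3 defines is time to first dose reduction, in patients starting on full dose.

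**Working it through.** The plan states no figure for this point, so there is nothing to reproduce. The check holds the hazard equal in everyone and varies follow-up alone.

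**Inputs from the documents.** Roll-over follow-up: 156 weeks (the stated minimum). New-patient follow-up: 76 weeks at least. Recruitment over 18 months, about 78 weeks, puts the longest at about 76 + 78 = 154 weeks, so a uniform spread over 76 to 156 weeks is reasonable.

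**Assumptions.** The hazard λ is constant, with 30% having an event by week 52: λ = −ln(0.7)/52 = 0.006859 per week, 1/λ = 145.8 weeks. The share of placebo roll-overs in Group 1, followed for 156 weeks, is 0, 20% or 40%. Early treatment discontinuation is ignored.

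**Formulas for fixed follow-up c.**
- Mean of all times, censored included: (1 − exp(−λc))/λ.
- Mean among events only: 1/λ − c·exp(−λc)/(1 − exp(−λc)).

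**Follow-up of 156 weeks.** exp(−156λ) = 0.7³ = 0.343.
- All times: 0.657 × 145.8 = 95.8 weeks.
- Events only: 145.8 − 156 × 0.343/0.657 = 145.8 − 81.4 = 64.3 weeks.

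**Uniform 76 to 156 weeks.** exp(−76λ) = 0.594. The average of exp(−λc) is (0.594 − 0.343)/(80λ) = 0.457, so 54.3% have an event.
- All times: 0.543 × 145.8 = 79.2 weeks.
- Events only: the average of c·exp(−λc) over the range is 51.3 weeks, so (79.2 − 51.3)/0.543, which is 51.2 weeks before rounding of the inputs.

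**Group 1 with placebo roll-overs.** The all-times means are weighted by patients, the events-only means by expected events.

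| Follow-up | Mean, all times (weeks) | Mean, events only (weeks) |
|---|---|---|
| 156 weeks | 95.8 | 64.3 |
| Group 1, no placebo roll-overs | 79.2 | 51.2 |
| Group 1, 20% placebo roll-overs | 82.5 | 54.3 |
| Group 1, 40% placebo roll-overs | 85.8 | 57.1 |
| Everyone at 76 weeks | 59.2 | 34.7 |

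The spurious gap to 156 weeks is 64.3 − 57.1 = 7.2 to 64.3 − 51.2 = 13.1 weeks for events only, and 95.8 − 85.8 = 10.0 to 95.8 − 79.2 = 16.6 weeks for all times. A simulation with 200,000 patients per scenario agrees to within about 0.1 week.

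**Other hazards.** From 20% to 60% with an event by week 52, and no placebo roll-overs, the events-only means run from 69.4 against 54.5 weeks down to 46.1 against 39.3. The all-times means run from 113.7 against 90.7 down to 53.1 against 48.8. The direction never changes.

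**Extreme case.** At 0.3 per year (1/λ = 173.9 weeks, 52.18 weeks per year) with all of Group 1 at 76 weeks:
- Events only, 76 weeks: 173.9 − 76 × 0.646/0.354 = 35.2 weeks.
- Events only, 156 weeks: 173.9 − 156 × 0.4078/0.5922 = 66.5 weeks.
- All times: 61.6 and 103.0 weeks.

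**Categories, censored times included, 30% case.** Bins up to 76 weeks agree to within about 0.1 percentage point. Beyond that they diverge. The bin from 76 to 88 weeks holds 4.7% at 156 weeks of follow-up and 12.9% for new patients. The 34.3% still event-free at week 156 fall in the last bin (over 156 weeks) if last intake is after day 1092, and in the bin below if it is on or before that day. New patients contribute 0% to the last bin. With 20% and 40% placebo roll-overs, Group 1 has 6.9% and 13.7% there.

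**Kaplan-Meier under the same hazard.** The first quartile is −ln(0.75)/λ = 41.9 weeks and the median ln(2)/λ = 101.1 weeks. Neither moves with follow-up, although the median is not reached if everyone stops at 76 weeks.

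**The case against.** The strongest reply is that the right analysis is already there. The paragraph after the mean plans Kaplan-Meier quartiles for time to first interruption, first dose reduction and premature discontinuation. That stands: nothing valid is missing, and the defect is one misleading extra display.

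Several limits on the point also stand.
- The 35 against 66.5 weeks of the extreme case should not be read as the expected effect. Seventy-six weeks is a minimum, entry is staggered, and Group 1 includes placebo roll-overs who are asked to stay at least 156 weeks.
- The early categories are hardly affected. Even in the later bins, the duration-of-exposure table in the same categories lets a reader see the follow-up.
- A reader might infer that a mean time to first dose change is planned. No such variable is defined, and the sentence on dose changes may refer only to counts and reasons.
- Nothing is tested, SAP 7.4 rules out a treatment comparison, and Protocol 7 warns of selection bias. Group 2 is selected for having stayed on treatment in the parent trial, so an equal hazard is a device for isolating the artefact and not a forecast.

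None of this makes the mean interpretable. It is specified by group and fails on either reading.

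**Conclusion.** The point holds, as a minor one. The mean in SAP 7.7 estimates no useful quantity and tends to be lower in Group 1 because new patients are observed for less time. Under the assumptions above, the spurious gap is about 7 to 13 weeks if only events are averaged and about 10 to 17 weeks if censored times are included. The size depends on a hazard and a Group 1 mix that the documents do not give. The direction depends only on Group 1 having shorter follow-up.

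A reader might infer that the trial's main tolerability conclusion is at risk. The documents do not support that. The primary endpoint is the incidence of treatment-emergent adverse events, analysed under SAP 7.4 and 7.8; adverse-event rates are also given per 100 patient-years; and the censoring-aware summary of these times is already planned.

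**What to change.** - In SAP 7.7, delete the mean for time to first interruption. State that the similar summary for dose changes contains no mean time, and that the only time variable involved is time to first dose reduction in patients starting on full dose.
- Keep the Kaplan-Meier quartiles as the summary of these times.
- In the category table of 5.4.3 and 7.7, show patients with an event and censored patients in separate columns, which preserves the useful early-onset counts. Alternatively, replace the table with Kaplan-Meier cumulative percentages at fixed weeks (for example 24, 52, 76, 104 and 156) with numbers at risk, by group. This also helps where the median is not reached: with 30 patients and 20% having an event by week 52, the median was estimable in only 39% of simulated samples.

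The cost is SAP wording and one table shell. No new data are needed.

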7.8 SAFETY ANALYSIS

All safety analyses will be performed on the treated set.

The analysis of safety data will be based on the concept of treatment emergent AEs or measurements. That means that, for analyses over the whole trial, all AEs/laboratory or vital sign measurements occurring between first nintedanib intake till last nintedanib intake + 28 days will be assigned to the on-treatment period.

All analyses will be performed by patient group and overall.

7.8.1 Adverse Events

Adverse events will be coded using the current Medical Dictionary for Regulatory Activities (MedDRA) version in use at BI at the time of database lock. The analyses of AEs will be descriptive in nature.

All analyses of AEs will be based on the number of patients with AEs and NOT on the number of AEs.

All AEs occurring before first drug intake in extension trial will be assigned to 'Screening period' and all AEs occurring after the residual effect period will be assigned to 'Follow-up period' (for patient data listings only).

For further details on summarisation of AE data, please refer to ([7](#), [10](#)).

According to ICH E3 ([11](#)), in addition to Deaths and serious adverse events, 'other significant' AEs need to be listed in the clinical trial report. These will be any non-serious adverse event that led to an action taken with study drug (e.g. discontinuation or dose reduced or interrupted). An overall summary of adverse events will be presented.

Adverse events related to gastrointestinal perforation, bleeding and hepatic injury, pathological findings identified on bone imaging and stunted growth identified on dental imaging are considered as protocol-specified AEs of special interest (AESIs) (see CTP Section 5.2.7.1.4), and are ticked as such in the eCRF.

The frequency of patients with AEs will be summarised by patient group and overall, primary system organ class and PT (mention MedDRA levels to be displayed in the tables). Time at risk and exposure-adjusted incidence rates per 100 patient years of AEs by patient group and overall will be presented in addition. Please refer to [Section 7.8.1.2](#) for further details on the derivation of time at risk and exposure-adjusted incidence rates.

The system organ classes will be sorted according to the standard sort order specified by EMA, PTs will be sorted by decreasing frequency (within SOC) in the total column.

Separate tables will be provided for patients with

- serious AEs (SAEs)
- severe AEs
- other significant AEs
- AEs leading to dose reduction
- AEs leading to permanent treatment discontinuation
- investigator defined drug-related AEs
- AEs leading to death
- protocol-specified AEs of special interest (AESIs) (as ticked on the eCRF AE page)
- Investigator defined drug-related SAEs

Adverse event groupings by safety topic have been defined outside the trial protocol, which will be continuously updated at project level ([12](#)). These safety topics are deemed of particular importance, and these definitions can be based on selection of coded terms based on MedDRA. The latest approved version of the project level overview archived prior to the respective DBL will be used in the CTR.

The frequency of patients with adverse events within these groupings will be summarised by system, safety topic, subcategory (if applicable) and preferred term. These displays will focus on patients with any adverse event, patients with serious adverse events and patients with investigator defined drug-related adverse events.

Systems will be presented in alphabetical order. Safety topics, subcategories (if applicable) and preferred term will be sorted by decreasing frequency in the total column (within system, safety topic or subcategory).

7.8.1.1 Adjudicated adverse events

An independent adjudication committee will review all fatal cases and adjudicate cause of death to respiratory, cardiovascular or other. The adjudication committee will also review all AEs categorised as MACE according to the definition in the adjudication charter.

In addition to standard safety analyses, the frequency of patients with AEs leading to death will be summarised by treatment, adjudicated cause of death (Cardiovascular, Respiratory or Other), and PT.

The frequency of patients with AEs categorised as MACE (that is all AEs categorised as MACE and therefore sent for adjudication) will be summarised by patient group and outcome

of adjudication (adjudicated as MACE or adjudicated as not MACE). The frequency of patients with AEs adjudicated as MACE will also be summarised by patient group and PT.

7.8.1.2 Exposure adjusted analysis of adverse events

Time at risk and incidence rates per 100 patient-years will be calculated based on the first onset of an AE in the trial.

For a specific AE, the total AE time at risk [years] is defined as

$$\frac{\text{Sum of time at risk across all contributing patients [days]}}{365.25}$$

with for each patient the time at risk [days] is defined as follows:

- *Date of first onset of the AE – date of first study drug intake [days] + 1 day* for patients with the specific AE,
- *End of time at risk – date of first study drug intake [days] + 1 day* for patients without the specific AE.

The end of time at risk is defined as the minimum of

- date last trial drug intake + 28 days
- derived date of last contact (for definition see [Section 5](#))
- date of death
- date of (interim) database lock.

The AE incidence rate [1/100 patient-years (pt-yrs)] will be calculated as

$$\frac{100 \times (\text{Number of patients with specific AE})}{\text{Total specific AE time at risk [years]}}$$

7.8.1.3 Adverse events with additional information collection

Diarrhoea, bleeding and ILD are AEs with additional AE-specific information collected on the eCRF. These are investigator reported on the eCRF and will be identified using this information for this analysis. That is if the diarrhoea information has been completed for an adverse event then the adverse event will be considered as diarrhoea for this analysis regardless of subsequent MedDRA coding of the verbatim term. Likewise, if the bleeding information has been completed for an adverse event then the adverse event will be considered as bleeding for this analysis regardless of subsequent MedDRA coding of the verbatim term. The same applies to ILD.

The frequency of patients with AEs with additional information collection will be summarised by patient group and overall, primary SOC and PT and separately for diarrhoea, bleeding and ILD. The additional information collected will also be summarised at the AE level (occurrence level) rather than at the patient level separately for diarrhoea, bleeding and ILD.

For the time to first onset of diarrhoea, bleeding or ILD, respectively, Kaplan-Meier plots by treatment will be created taking into account the respective data over the whole trial. The same censoring rules as for time to first liver enzyme elevation will be used, see [Section 5.4.4.1](#) for details.

7.8.1.4 Pathological findings of epiphyseal growth plate on imaging, on dental examination or dental imaging

Adverse events identified based on imaging or dental examination will be reported in the Adverse Event page of the eCRF and will be listed in the standard AE tables and patient data listings.

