5.2.7.1.5 Intensity (severity) of AEs

The intensity (severity) of the AE should be judged based on the following:

- Mild: Awareness of sign(s) or symptom(s) that is / are easily tolerated.
Moderate: Sufficient discomfort to cause interference with usual activity.
Severe: Incapacitating or causing inability to work or to perform usual activities.

In addition, the intensity (severity) of diarrhoea adverse events should be classified and recorded in the eCRF according to the Common Terminology Criteria for Adverse Events (CTCAE) version 5 on an additional diarrhoea adverse events eCRF [[R18-1357](#)]. See Table 5.2.7.1.5: 1. below.

Table 5.2.7.1.5: 1 CTCAE Categorization for diarrhoea

CTCAE Grade	Diarrhoea
1	Increase of <4 stools per day over baseline
2	Increase of 4 to 6 stools per day over baseline
3	Increase of ≥ 7 stools per day over baseline; incontinence
4	Life threatening consequences
5	Death

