5.2.7.2.4 Safety monitoring and adverse events with additional information collection

- An external expert in radiology will review all MRI/radiological assessments (bone imaging). Additionally, images of a particular patient may be reviewed by other radiology or clinical experts selected by the sponsor for consultancy, if judged needed by the sponsor to assess safety of this particular patient or to support overall safety assessment.
- A blinded external expert in paediatric dentistry will review all panoramic x-rays (dental imaging). Additionally, images of a particular patient may be reviewed by other external dentist/expert in paediatric dentistry selected by the sponsor for consultancy, if judged needed by sponsor to assess safety of this particular patient or to support overall safety assessment.
- An independent SMC will conduct regular reviews of the trial safety data, with access to any data including MRI/radiological assessments, height measurements, and panoramic x-rays, as detailed in [Section 3.1](#), in [Section 5.2.5](#) and in the SMC charter.
- An independent Adjudication Committee (AC) will review all fatal cases and adjudicate all deaths to either cardiac, respiratory or other causes and will review all adverse events categorized as major adverse cardiovascular events (MACE). MACE is defined as non-fatal myocardial infarction, non-fatal stroke and cardiac death. In parallel, the Adjudication Committee/a member of the Adjudication Committee will review all dental findings of stunted growth of the dental root identified by central review to assess them to either pathological finding /stunted growth or not. Certain further dental findings on dental imaging may potentially be assessed if defined in the Adjudication Charter (dental imaging from 1199-0337 study may be included in this assessment process).

- Additional details (on top of standard AE and SAE reporting) will be collected in the eCRF for the adverse event ‘diarrhoea’ and the adverse events in the subordinate Standard MedDRA Query (SMQ) ‘Haemorrhage terms, excluding laboratory terms’.

[figure not shown]

[figure not shown]

[figure not shown]

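### SAP 7.8.1.3 selects diarrhoea, bleeding and ILD events by completion of the extra eCRF information and does not reconcile this with MedDRA coding, so coded events without it are missed in its frequency table and Kaplan-Meier plots

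*SAP*

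**What the plan says.** **Protocol, data collection.** Section 5.2.7.2.4 requires additional eCRF details for the adverse event diarrhoea and for "the adverse events in the subordinate Standard MedDRA Query (SMQ") called Haemorrhage terms, excluding laboratory terms. For diarrhoea, Section 5.2.7.1.5 adds that the CTCAE grade is recorded "on an additional diarrhoea adverse events eCRF".

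**SAP, analysis.** Section 7.8.1.3 covers diarrhoea, bleeding and ILD. Its selection rule is: "These are investigator reported on the eCRF and will be identified using this information for this analysis". For bleeding it adds that "if the bleeding information has been completed for an adverse event then the adverse event will be considered as bleeding for this analysis regardless of" the later coding of the verbatim term. Diarrhoea and ILD are treated the same way.

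Three outputs rest on this selection:
- a patient-level table: "The frequency of patients with AEs with additional information collection will be summarised by patient group and overall, primary SOC and PT and separately" for each of the three event types;
- an occurrence-level summary of the extra details;
- time-to-event plots: "For the time to first onset of diarrhoea, bleeding or ILD, respectively, Kaplan-Meier plots by treatment will be created". Censoring follows the liver-enzyme rules in SAP 5.4.4.1.

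**SAP, other displays.** Section 7.8.1 tabulates all adverse events by system organ class and preferred term, with rates per 100 patient-years. It has a separate table for "protocol-specified AEs of special interest (AESIs) (as ticked on the eCRF AE page"), and bleeding is one of these. It also plans safety-topic groupings, which may use coded terms; their specification is held outside the documents.

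**The concern.** The set of events for which the protocol wants the extra page is fixed, for bleeding, by MedDRA coding. The set that the SAP analyses is fixed by whether the page was filled in. The SAP itself describes coding as coming later, so the page may be completed or omitted before the preferred term is known. The two sets agree only if every qualifying event receives a page. The plan has no step that adds coded events without one, compares the two sets, or repeats the analysis by code.

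Bleeding is an adverse event of special interest (Protocol 5.2.7.1.4), and Protocol 4.2.1.1 describes diarrhoea as the drug's most frequent side effect. At stake are the share of patients with such an event and the timing of its first onset, as shown in SAP 7.8.1.3. A report could also show page-based, tick-box-based and code-based counts of bleeding that differ, with no rule to explain the difference.

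**Working it through.** **Step 1. Follow an event through the rules.** Take an adverse event coded to the haemorrhage sub-SMQ, or to diarrhoea, whose extra page was not completed.

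| Output | Selected by | Event included? |
|---|---|---|
| Primary endpoint and tables by system organ class and preferred term (SAP 7.4.1, 7.8.1) | all treatment-emergent events | yes |
| Exposure-adjusted rates (SAP 7.8.1.2) | first onset of the coded event | yes |
| AESI table, bleeding only (SAP 7.8.1) | tick box | if ticked |
| Safety-topic tables (SAP 7.8.1) | may be coded terms | cannot be determined |
| Patient-frequency table (SAP 7.8.1.3) | page completed | no |
| Kaplan-Meier plot (SAP 7.8.1.3) | page completed | no |

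If this was the patient's only such event, the patient is missing from the frequency table. In the plot the patient is censored at the earliest of last intake plus 28 days, last contact, or death. If a later event has a page, the patient is counted but with too late an onset. In the other direction, an event with a page but coded elsewhere is counted.

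**Step 2. Scale of one missed patient.** The plan has no figure to reproduce on this point. The protocol synopsis gives about 50 to 60 patients.
- 100/50 = 2.0 points; 100/60 = 1.7 points.
- In a patient group of 20 to 30 (assumed): 100/20 = 5.0 points; 100/30 = 3.3 points.

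**Step 3. Illustration under stated assumptions.** The documents give neither event nor page-completion rates. Let p be the true share of patients with the event, c the chance that an event has its page, and k the events per affected patient, with pages missing independently. The share shown is p × (1 − (1 − c)^k).

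For k = 1, share shown (expected patients missed out of 50, which is 50 × p × (1 − c)):

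| True share p | c = 95% | c = 90% | c = 80% |
|---|---|---|---|
| 20% | 19.0% (0.5) | 18.0% (1.0) | 16.0% (2.0) |
| 40% | 38.0% (1.0) | 36.0% (2.0) | 32.0% (4.0) |
| 60% | 57.0% (1.5) | 54.0% (3.0) | 48.0% (6.0) |

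At p = 40% and N = 50 there are 20 affected patients. The chance of missing at least one is 1 − c^20, which is 64%, 88% and 99% at 95%, 90% and 80% completion.

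For k = 3 and c = 80%, the share shown is 40% × (1 − 0.2³) = 39.7%, almost unchanged. Timing still suffers: the chance that the first event lacks a page but a later one has it is 0.2 − 0.2³ = 0.192, so about 0.192 × 20 = 3.8 of the 20 affected patients would have their onset placed too late.

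At c = 100% nothing is lost. The illustration counts losses only. Events with a page but coded elsewhere act the other way, so the net direction is not known.

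**The case against.** **Protocol and SAP are not in direct conflict.** A reader might infer that the protocol defines bleeding by a MedDRA query and that the SAP overturns the definition. The documents do not support that. Protocol 5.2.7.2.4 says which events receive extra data collection. The AESI list in 5.2.7.1.4 names bleeding without a query, and Protocol 7.2.6 sets no query-based bleeding analysis. What remains is a gap within the SAP. The SAP also states only that a completed page makes the event count; exclusion of events without a page is an inference from its selection sentence, though the natural one.

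**The section has a narrow purpose.** It reports events with additional information, so selection by page is right for the summary of page content. This stands for the occurrence-level summary. It does not cover the patient-frequency table or the plots, which would be read as the frequency and timing of bleeding and diarrhoea.

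**The events appear elsewhere.** This stands and limits the reach of the point. Nor can these plots be called the only curves for first bleeding or diarrhoea, because SAP 7.6.3 refers to endpoints in Section 5.3.2, which is not visible.

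**No loss is shown.** The eCRF design, completion instructions and data-management queries are not in the documents. Sites can recognise bleeding clinically, and its AESI status is a further prompt. This stands too: the loss is possible, not demonstrated. But the documents describe no check that would prevent or reveal it.

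**Conclusion.** The point holds for two outputs, the patient-frequency table and the time-to-first-onset plots in SAP 7.8.1.3. Both depend on complete page entry, and the plan describes no check of this against coding. For bleeding and diarrhoea, a qualifying coded event without its page is left out or delays the apparent onset. ILD is selected in the same way, although the visible text of Protocol 5.2.7.2.4 does not list it for extra collection.

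The size cannot be established from the documents. Each missed patient costs 2.0 to 1.7 points overall. The larger figures above rest on assumed event and completion rates; with several events per patient the percentage hardly moves and the effect falls on timing.

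A reader might infer that overall adverse-event incidence is understated. It is not: the primary endpoint, the standard tables and the exposure-adjusted rates do not use the page. The trial is descriptive with no testing, so no decision rule is affected. This is an inexpensive improvement to the consistency of the safety report.

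**What to change.** In SAP 7.8.1.3, for the patient-frequency table and the Kaplan-Meier plots:
- count an adverse event as bleeding if the bleeding page is completed **or** its preferred term is in the sub-SMQ named in Protocol 5.2.7.2.4;
- count it as diarrhoea if the diarrhoea page is completed **or** it is coded to diarrhoea;
- make the same page-versus-coding check for ILD, after naming the coded terms to compare against.

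Keep the page-based set for the occurrence-level summary of page details such as CTCAE grade. List every event where page and coding disagree, including those with a page but coded elsewhere. The combined rule still counts the latter, so the listing is what makes a wrongly opened page visible.

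The cost is SAP wording and a short derivation, with no new data. The SAP already uses coded terms in a similar way to find symptoms of hepatic injury (5.4.4 and Table 10.5: 1). The downside is that some counted events will have missing page details.
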